Children's exposure to violent and nonviolent discipline was assessed using the MICS Child Development and Child Disciplinary modules. Exposure to violent disciplinary practices was defined as having experienced as a cumulative score of the number of forms of violent discipline

Intimate Partner Violence

Intimate partner violence among parents who are currently married, cohabitating, and/or in a relationship was assessed using an adapted and abbreviated version of the revised Conflict Tactics Scale (CTS-2: Strauss, 2004) previously used in Rwanda (Chaudhury et al. 2016). The CTS-2 assesses caregivers' self-reported victimization and perpetration of emotional neglect/abuse, physical assault, and sexual assault. Given the short interval between the baseline and midline data collection, the scale was adapted so that caregivers report on events that occurred within the last three months and ever (as opposed to 12 months in the original scale). For events that had happened, caregivers further report on the frequency of that event using the following scale: 0="not at all"; 1="once"; 2="Twice"; 3="3-5 times"; 4="6-10 times"; 5="11-20 times"; 6=">20 times." Overall, the same events are asked for victimization and perpetration with the exception that two additional sexual assault questions were asked about for victimization (detailed below). The following examples refer to victimization. After the questions about victimizations, caregivers were asked similar question for perpetration stated as "You [left you or forgot] your partner" etc.

Two items assess emotional abuse or neglect: "Your partner used abusing language toward you" and "She/he left you or forgot you." Seven items assess physical abuse : "She/he shoved you,"

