VUP-status [classic public works vs. expanded public works]	Government records
OUTCOME VARIABLES	
Malawi Developmental Assessment Tool (MDAT)	
Gross motor [standardized score]	MDAT
Fine motor [standardized score]	MDAT
Language [standardized score]	MDAT
Social [standardized score]	MDAT
Ages and Stages Questionnaire (ASQ-3)	
Gross motor [delayed/not delayed]	ASQ-3
Fine motor [delayed/not delayed]	ASQ-3
Communication [delayed/not delayed]	ASQ-3

Personal social [delayed/not delayed]	ASQ-3
Problem solving [delayed/not delayed]	ASQ-3
Anthropometrics	
Height-for-age (HAZ)	Anthropometrics
Weight-for-age (WAZ)	Anthropometrics
Weight-for-height (WHZ)	Anthropometrics
Middle upper arm circumference (MUAC)	Anthropometrics
"Father engagement "	
" father spends time every day caring for the child"	HOME
Family Violence	
Violent discipline [cumulative score, 0-7]	MICS-5 Hash discipline module
Intimate partner violence	
Victimization physical and sexual abuse past 3 months [cumulative score 0-7]*	Conflict Tactics Scale- CTS2
Perpetration physical and sexual abuse past 3 months [cumulative score 0-7]**	Conflict Tactics Scale- CTS2

*Among cohabitating or married mothers only

**Among cohabitating or married fathers only

***Among cohabitating or married caregivers only

Table 2. Study predictor and outcome variables.

Data Analysis Plan

Standard descriptive statistics will be used to describe the study sample. Frequencies and percentages will be reported for categorical variables and mean, median, standard deviation, interquartile range, maximum and minimum values will be reported for continuous variables. Anthropometric data will be cleaned for extreme out-of-range values. Scales will be created from individual items according to scoring instructions for each scale. All scales will be evaluated for psychometric properties. Visual inspection of histograms and other plots will be used to identify outliers.

Continuous Outcomes MDAT, WAZ, MUAC, WHZ: The goal is to determine the efficacy of SM at 12 months from study initiation. Measurements of all outcome variables (see Table 2 and Section B), are taken at baseline, midline (4 months post baseline), and endline (12 months post midline). Subjects are randomized (Section B) into a treatment group (SM) and CG. Effectiveness will be determined if the slope of the response variable for the SM group is significantly different than the slope of the CG group. To test this hypothesis, we will fit a linear

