assumption does not hold across time (baseline, 3 months, and 12 months) we can treat time as a categorical variable to examine differences between the treatment groups at individual time points focusing on the 12-month group differences adjusted for baseline. If examination of panel plots reveals a large amount of heterogeneity among trajectories of the outcomes by subjects we can use Growth Mixture Models which first identify clusters of similar trajectories from which we can test for treatment group differences in terms of membership in the clusters of similar trajectories.

Outliers will be flagged through visual inspection and standardized residual values greater than 3. A sensitivity analysis will be done to determine if outlier removal changes the coefficient values. If we find that outliers are having an oversized effect on the estimated coefficient values we will give preference to the models where the outliers are removed. However, we will present both results.

Some responses are scales or derivations of scales in particular the MDAT and the ASQ. We will examine the psychometric performance of these scales. We are especially concerned with internal consistency and item reliability. If these scales do not show at a minimal amount of internal consistency (Cronbach's Alpha > 0.6) these items will not be considered for analysis. If particular items are an issue they may be dropped from the scale. Research, in areas like Rwanda suffer because standard scales have not been validated on these populations.

Binary Outcome ASQ, shared decision making, father engagement: The analysis for these outcomes will be similar to the analyses above with accommodations being made for the fact the ASQ is a binary outcome. In particular, we will have to make use of mixed effect logistic regression models a form of generalized linear mixed models (GLMM) with a binomial distribution and a logistic link. Outside of accounting for the correct distribution of the response variable the analysis will follow the methods outlined in the previous MDAT section.

Model Assumptions and Alternative Tactics: We will examine Pearson residuals to assess goodness of fit. Alternative methods include the use of quasi-binomial mixed effects regression (in the case of over dispersion). However, such models do not have a full likelihood and instead of LRT test we will have to rely on the Wald-type type test for regression coefficients.

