In fitting logistic mixed effect regression models, it is possible that we may run into numerical difficulties in computing a likelihood ratio test, so score type tests may be needed. This is more likely to occur in the case of testing for variance components.

Count Outcomes, harsh discipline, physical and sexual violence: These metrics count types of harsh discipline action or physical and sexual abuse as suffered or inflicted. Our experience with these scales is that there are more values of zero than what would be predicted by a standard

Poisson distribution. Our analysis will make use of Zero Inflated Poisson (ZIP) models (Everitt, & Hothorn, 2005; Long, 1997). These models belong to the more general class of mixture models. In particular they model the binomial probability of a count of zero versus a count greater than zero and the Poisson probability for counts greater than zero. In particular we will fit mixed effect models as described in the continuous variable sections but under the ZIP distribution assumption.

A key difference between a mixture model and more standard probability distributions is the fixed effects structure and tests for significance can vary between the two parts (binomial and Poisson). Likelihood ratio testing for the Time*Treatment group interaction will be performed for both components of the mixture model. A significant result of the LRT test for the binomial portion would indicate that the probability of no violence (inflicted or suffered) differed between the treatment groups. A significant result of the LRT on the Poisson portion of the ZIP model would indicate that among those who inflicted or suffered harsh discipline or violence the mean amount of violence differed between the treatment groups. The two portions are contained in a single likelihood function and parameter estimation is done simultaneously.

Model Assumptions and Alternative Tactics: The key assumption in these models is the ZIP distribution of the response variables. We will visually inspect the distribution of the outcome variables to verify that we are fitting the correct model. Alternative distributions could be Poisson, Quasi-Poisson, Binomial (data dichotomized due to lack of variability), or Negative Binomial. These are non-mixture models and modeling will follow the process outlined in the continuous outcomes section.

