Secondary Outcomes: Stunting measured by Height-for-Age is an important outcome. However, we do not expect to see significant changes in this variable in the 12-month timespan. We do expect to see a reduction in stunting even if it does not achieve statistical significance. Using the models described in data analysis plan we can extract the coefficient for the time by treatment group interaction as an estimate of the size of the effect of SM on stunting. Effect sizes of other secondary outcomes will be reported similarly.

Missing Data

We will apply the ITT principle to all of our analyses. Unless a subject dies, the ITT convention is to keep them in the study; HLM handles this well since the linearity assumption allows us to estimate subject-specific parameters so long as we have at least two data points. The method of mitigating bias due to missingness known as full-information maximum likelihood estimation (FIMLE) can be problematic in mixed effects linear models. Principled methods of multiple imputation such as chained equations will be employed.

Power and Sample Size

Assuming the linear mixed effect model described above. The following values were used to calculate statistical power. We assumed a total of 200 clusters with 5 families per cluster. We assume a linear relationship over time. The significance level is set at 0.05. The statistical test was the likelihood ratio test for the inclusion of the time by treatment group interaction. The ICC was set at 0.10. A variable for public works type which was categorical with 3 levels was included in the model. Within public works type a ratio 1:1:2 for expanded:both:classic was assumed. Variability was set to one so that effect sizes may interpreted as “Cohen-Like” effect sizes. We found that we have at least 90% power to detect an effect size of 0.25 and at least 80% power to detect an effect size of 0.22. GLIMMSE software was used for these calculations.

E. Safety & Adverse Events

Risks to Subjects

The following risks were identified and submitted to the Boston College IRB:

1. Participation in the intervention may lead adults to confront stressful personal or family issues or generate concern about social harm resulting from loss of confidentiality, which may elicit distress in some participants.
2. In some cases, fatigue from the psychosocial assessment administered pre/post-intervention and at 12-months follow-up may occur.
3. There is a small risk of loss of confidentiality.

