4. Participation in the intervention may create issues within the community if a household receiving the SM intervention is viewed as receiving additional services or monetary support.

We consider most risks associated with participation in the study to be unlikely. Two previous pilots of SM have been carried out with vulnerable families in Rwanda. Previous study iterations have demonstrated that processes related to confidentiality are upheld throughout the entire study. Further, no participants have indicated distress or fatigue with the assessments. Weekly field reports from the Laterite enumerators have not indicated any issue with the assessments, length of time to administer, issues with confidentiality, or distress caused.

There are other risks we consider to be likely: intimate partner violence in the home and tensions with neighbors due to participation in the intervention. The CBVs have received comprehensive training on recognizing intimate partner violence in the home as well as how to activate our risk of harm protocol to ensure we assess the harm and make the necessary referrals. The other risk related to community tensions due to participation have resulted in several study changes. First, in the event that an issue arises with a neighbor, the CBV immediately alerts their supervisor and the village leader or elder to better understand the source of the issue. During this time, the intervention is paused. The family is then given the option to conduct the intervention

offsite at the local government offices at the cell level. As a preemptive measure, all supervisors have traveled to the field to meet with the village leader and Cell official to further communicate the SM as a coaching intervention and not an intervention where goods or money are provided to families.

Monitoring

A Risk of Harm decision tree, along with flagged questions from the assessment battery, provides a structured protocol for monitoring and responding to adverse effects on participants. Interventionist supervisors have daily phone check-ins with the interventionists as well as weekly face-to-face meetings. These check-ins provide an opportunity for monitoring families in the study and ensuring all study risks are addressed appropriately. Further, these check-ins allow the supervisor to anticipate any potential risks and work with the interventionist to initiate support or a referral to mitigate any potential risks.

Stopping Procedures if relevant.

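### Partner violence is compared between arms only by a linear slope, so a midline rise that fades by endline is missed or, with time in months, moves the test toward benefit

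*Combined protocol and SAP*

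**What the plan says.** - **Risk.** Section E, Risks to Subjects: "There are other risks we consider to be likely: intimate partner violence in the home". The response described there is training the home visitors to recognise such violence, a risk-of-harm protocol and referral.
- **Outcome.** Hypothesis 1(c) expects less family violence, including partner violence, under SM. Table 2 lists "Victimization physical and sexual abuse past 3 months" for married or cohabiting mothers, and the matching perpetration score for fathers.
- **Test.** Section D, Count Outcomes: "Likelihood ratio testing for the Time*Treatment group interaction will be performed for both components of the mixture model". The models are those of the continuous-outcomes section, refitted under a ZIP distribution. That section has treatment, time as a single term, and their product. Its decision rule is: "Effectiveness will be determined if the slope of the response variable for the SM group is significantly different". Power and Sample Size adds: "We assume a linear relationship over time".
- **Fallback.** If linearity fails, time may be made categorical to compare the arms "at individual time points focusing on the 12-month group differences adjusted for baseline".
- **Dates.** The Data Analysis Plan has "midline (4 months post baseline), and endline (12 months post midline", that is 0, 4 and 16 months. The linearity fallback has 0, 3 and 12. Study Visits and the heading on other midline procedures put midline 4 months after the intervention. The CTS2 description says "Given the short interval between the baseline and midline data collection, the scale was adapted", giving a 3-month recall period.
- **Coding.** Whether time enters as months or as wave number is not stated. The measures heading numbers the waves 1 to 3.

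**The concern.** The midline CTS2 score may be the only partner-violence measure taken in both arms that looks back on the visits themselves. Endline, a year later with 3-month recall, cannot. A reader would expect a listed risk to be compared between arms at that wave, yet no such contrast is planned. The planned slope also does not treat midline neutrally: in a straight-line fit, a wave that falls before the mean of the three times pulls the slope the opposite way.

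The trial could therefore report lower partner violence for a programme under which violence had gone up at midline and then subsided. The same mechanism would penalise a real early reduction that wore off. Section D would read a significant interaction as a difference between the arms without naming a wave, so the report need not reveal either pattern.

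**Working it through.** **The plan's own figure.** Power and Sample Size gives at least 90% power at an effect of 0.25 and at least 80% at 0.22, with 200 clusters of 5 and ICC 0.10. With 500 families per arm and design effect 1 + 4 x 0.10 = 1.4, effective n is 357 per arm and SE = sqrt(2/357) = 0.075. Power is 91.6% and 83.6%, so the statement reproduces. It assumes linearity and says nothing about effects at a single wave.

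**Weights.** For complete data, the fitted SM-minus-control change over trial length T is T x sum[(t - mean t) x d(t)] / sum[(t - mean t)^2], where d(t) is the arm difference at time t. On 0/4/16 the mean is 6.67, the deviations are -6.67, -2.67 and 9.33, and the sum of squares is 138.67. Multiplying each deviation by 16/138.67 gives the first row.

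| Time coding | Baseline | Midline | Endline | Break-even retention |
|---|---|---|---|---|
| 0/4/16 or 0/3/12 | -0.77 | -0.31 | +1.08 | 28.6% |
| 0/7/19 (3-month delivery, midline 4 months later) | -0.89 | -0.17 | +1.06 | 16% |
| 0/8/20 (4-month delivery, midline 4 months later) | -0.92 | -0.13 | +1.05 | 12.5% |
| Wave numbers 1/2/3 | -1 | 0 | +1 | 0% |

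Break-even is the midline weight divided by the endline weight, sign ignored: 0.308/1.077 = 0.286. A midline rise of which less than this share remains at endline gives a negative slope, which reads as benefit. On 0/4/16 the midline weight stayed negative when 10-50% of endline data were removed.

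**Example paths on 0/4/16** (midline, endline difference in SD, no baseline difference; values illustrative):
- (+0.30, 0): -0.092, toward benefit.
- (-0.30, 0): +0.092, against SM.
- (+0.30, -0.15): -0.092 - 0.162 = -0.254.
- (-0.15, -0.15): +0.046 - 0.162 = -0.115.
- (+0.30, +0.30): 0.30 x 0.769 = +0.231, harm.

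The third path, with a midline rise, scores about twice as well as the fourth, a steady reduction. With wave numbers both score -0.15 and cannot be told apart.

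**ZIP scale.** Assume structural zeros of 0.65 in every cell except SM midline, where they are 0.55, with Poisson mean 1.5. Any violence is then 27%, and 35% at SM midline. The logit of the zero probability drops from 0.619 to 0.201, a change of -0.418, and -0.418 x -0.308 = +0.13 log-odds of no violence. A large-sample ZIP fit gives the same +0.13, in SM's favour.

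**Recall coverage of delivery**, if delivery starts at baseline and lasts 3-4 months:
- Midline at 4 months: recall spans months 1-4, covering 2/3 = 67% or 3/4 = 75%.
- Midline 4 months after the intervention: 0%.
- Enumerator training dates (baseline ending 9 February 2018, refresher to 20 April, midline refresher to 8 August) suggest a gap of about 3.6 to 6 months if fieldwork followed training. At 6 months coverage is 0-25% and the midline weight on 0/6/18 is -0.21. Fieldwork dates are not given.

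**Detection among couples.** A count simulation assumed 300 couples per arm and any violence at 33%, rising to 41% or 46% at SM midline only. It used a Poisson fit with cluster-robust errors. The slope flagged harm in about 1% of trials or fewer, and benefit in 6% or 12%. A midline contrast flagged harm in 27% or 50%. Details of the set-up move these figures by several points.

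**Price of switching**, at constant within-family correlation and on 0/4/16. The slope change has relative SE sqrt(1.846) = 1.359, and a single-wave contrast sqrt(2) = 1.414. For an endline-only effect the z ratio is (1/1.414)/(1.077/1.359) = 0.89. For a sustained effect it is (1/1.414)/(0.769/1.359) = 1.25.

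**The case against.** Four arguments carry weight.

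1. **The slope is not reversed in general.** A reader might infer that any rise in SM homes counts as benefit. It does not: a sustained rise has weight +0.77 and reads as harm. Only a rise that mostly fades is misread. A reader might also take the negative weight as settled, but with wave numbers, which the plan does not exclude, it is zero and the test is blind rather than wrong-signed. This stands in full.
2. **Midline may not see delivery.** A reader might infer that midline captures most of the visits. That holds at 4 months after baseline and fails at 4 months after the intervention. The short-interval remark in the CTS2 description favours the earlier date but does not settle it.
3. **The risk sentence is ambiguous.** It may mean violence met in homes rather than caused by visits. Nothing in the documents predicts a transient rise, and the paths above are illustrations. The point does not need a causal reading: an outcome listed as a likely risk should be readable wave by wave.
4. **The plan has some protection.** It commits to checking assumptions and functional shape, and a midline spike is non-linear. However, the categorical option is discretionary, depends on judging plots, and is aimed at the 12-month difference. The decision tree, check-ins and referrals handle individual cases and do not compare arms.

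Higher detection rates would follow from using all 500 families per arm, but CTS2 is analysed only in partnered caregivers, so those rates should not be relied on.

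**Conclusion.** The gap is real and limited. The only planned between-arm test of partner violence cannot register a midline-only rise as harm under any schedule or coding that the documents allow, because the midline weight is never positive. It ranges from -0.31 to 0. With time in months, a rise retained below about 29% at endline (12.5-16% on the later midline dates) moves the result toward benefit. With wave numbers it goes unseen. The documents do not support saying that the intervention causes violence, that every rise is misread, or that midline certainly covers delivery. The weights are exact for complete data on a linear scale and approximate for the ZIP link. The detection rates rest on assumed prevalences and numbers of couples. This is a worthwhile, inexpensive improvement rather than a flaw that invalidates the analysis.

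**What to change.** For CTS2 victimization and perpetration:

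1. Fit time as a three-level factor from the start in both ZIP parts.
2. Name the endline-versus-baseline arm contrast as the test of Hypothesis 1(c).
3. Report the midline-versus-baseline arm contrast with a cluster-adjusted 95% confidence interval, whatever its sign, as a safety readout outside the alpha.
4. Fix one midline date, state what each 3-month recall window covers, and word the conclusion by wave.
5. Keep the linear slope as a sensitivity analysis, with the time coding stated.

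**Cost.** No new data or visits are needed: one extra interaction term per ZIP part and one more table row per wave. The z-score for 1(c) falls about 11% if the effect exists only at endline and rises about 25% if it is sustained.

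**Limits.** Power of the midline contrast among partnered caregivers is modest (about 27-50% on the assumptions above), so a null midline result should not be read as showing safety. The differential self-report that Section F warns of could also mask a rise in SM homes.
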